## 2 STUDY DESIGN AND FLOW

This is a post-approval, multi-center, double-blind, randomized, placebo-controlled, 2-way cross-over study assessing daridorexant at a dosing regimen of 50 mg, once daily, vs placebo over a 4-week treatment period in adult subjects of 55 years and older with insomnia and comorbid nocturia.

[figure not shown]
Approximately 50 subjects will be randomized in a 1:1 ratio to one of two treatment sequences: daridorexant 50 mg / placebo or placebo / daridorexant 50 mg.

The study will be conducted at approximately 18 sites in the United States, Spain, and Germany.

The study design is shown in Figure 1.

Page 9/50

Figure 1 Study design for ID-078A401

- The voiding diary is completed on 3 consecutive days following V1, V2 and V6 and on the 3 days immediately preceding V4 and V8
- <--> Daily completion of sleep diary from V1 to V8

D = day; EOS = end-of-study; EOTP = end-of-treatment period; V = visit.

The study comprises the following 5 periods: the screening period, TP I, washout period, TP II, and the safety follow-up period.

The **screening period** starts with the signing of the informed consent form at Visit 1 and ends with Randomization at Visit 2 or with a screening failure. It lasts 14–21 days.

**TP I** starts with the administration of the first dose of study treatment and ends on the day after the last dose of study treatment (Day 29). The study subjects will be treated for 4 weeks.

The **washout period** starts after completion of the TP I and lasts 14–21 days. During the washout period the subjects will not be treated at all and will be followed up for safety (5–10 days).

**TP II** starts with the administration of the first dose of the 'other' study treatment and ends on the day after the last dose of study treatment (Day 29). The study subjects will be treated for another 4 weeks.

The **safety follow-up period** starts on the day after the last dose of study treatment in TP II and ends at the EOS visit (5–10 days after EOTP II).

#### 3 OBJECTIVES

The overall objective of this post-approval study is to evaluate the clinical efficacy, safety, and tolerability of daridorexant 50 mg administered once daily, compared to placebo in adult subjects with insomnia and comorbid nocturia over a period of 4 weeks.

# 3.1 Primary objectives

The primary objective of this study is to assess the efficacy of daridorexant on insomnia variables in subjects with insomnia and comorbid nocturia.

# 3.2 Secondary objectives

The secondary objective is to assess the efficacy of daridorexant on nocturia variables.

# 3.3 Safety objectives

The safety objectives will be to assess the safety and tolerability of daridorexant.

#### 4 ANALYSIS SETS

# 4.1 Definitions of analysis sets

A study subject must have given informed consent before being included in any analysis set.

# 4.1.1 Screened analysis set

The SCR includes all study subjects who entered Screening and have a subject number.

Summaries based on the SCR set will be presented as one group (i.e., all study subjects), unless otherwise specified.

## 4.1.2 Randomized analysis set

The RND includes all study subjects from the SCR who were randomized (i.e., assigned to a treatment sequence).

#### 4.1.3 Full analysis set

The FAS includes all subjects from the RND who received at least one dose of double-blind study treatment.

To adhere to the intent-to-treat principle,

- Subjects will be evaluated according to their assigned study treatment, which may differ from the treatment they have received (in each treatment period).
- Unless otherwise specified all available data will be included in the analyses.

## 4.1.4 Per-protocol set

The PPS includes all subjects from the FAS without important PDs occurring during the screening/baseline assessments or prior to Week 4 (in both treatment periods, i.e., between

Visit 2 and Visit 4 in TP I, and between Visit 6 and Visit 8 in TP II), which could affect the analysis of the primary endpoint variable.

The following important PDs will lead to exclusion from the PPS:

- At least one key inclusion criterion (except #1) was not met (#3, #4, #5, #6, #7; PD Code: 01A02);
- At least one key exclusion criterion was met (#3, #6, #7, #8, #13; PD Code: 01B01);
- Incorrect blister dispensed to the subject and at least one tablet was taken (PD Code: 02A01);
- Failure to comply with IMP storage/retention requirements impacting the quality of the IMP, reported as 'not to be used' by the Quality Assurance department, and at least one tablet was taken by the subject (PD Code: 02B01);
- At least one IMP compliance value < 80% (PD Code: 02E01);
- Non-compliance with blinding procedure/maintenance with consequences of patient treatment / study arm revealed or easily identifiable (PD Code: 03D01);
- Sleep diary not completed at least 2 days during Screening and Week 4 of each treatment period (PD Code: 03G02);
- Treatment with forbidden medication (PD Code: 04A01).

Study subjects will be evaluated according to the treatment they have been assigned to. If only one of the two treatment periods of a subject is affected by one of the above PDs, the subject still will be completely excluded from the analysis as the deviation also might have an impact on the second treatment period (e.g., forbidden medication with a long half-life or similar).

#### 4.1.5 Safety analysis set

The SAF will include all subjects who received at least one dose of double-blind study treatment. Subjects will be analyzed based on the treatment received (in each period).

## 4.2 Analysis

The number of study subjects in each analysis set defined above will be tabulated by treatment sequence (daridorexant 50 mg / placebo or placebo / daridorexant 50 mg) and overall. Any study subject excluded, along with the reason(s) for exclusion from the PPS, will be summarized and listed.

# 4.3 Usage of the analysis sets

The analyses of the primary endpoint and all other efficacy endpoints will be performed using the FAS.

The analyses of the primary endpoint will be repeated based on the PPS.

The SAF will be used for the analysis of safety endpoints (including previous and concomitant medications, and study treatment exposure).

The SCR is used to provide the same summaries for the screen failures.

Subject disposition will be described based on the SCR.

Study subjects' data will be listed using the SCR, unless otherwise specified.

Of note, there are no baseline disease characteristics collected in this study other than baseline values of efficacy and safety variables.

Table 2 Usage of analysis datasets

Analysis	SCR	RND	FAS	PPS	SAF
Subject disposition	X				
Demographics / Baseline Characteristics		X*	X*		
Previous and concomitant medication					X
Study drug exposure					X
Efficacy analysis			X	X	
Safety and tolerability analyses					X

FAS = full analysis set; PPS = per-protocol analysis set; RND = randomized analysis set; SAF = safety analysis set; SCR = screened analysis set.

### 5 SUBJECT VARIABLES AND ANALYSES

Due to the cross-over design, each subject will contribute to both treatment columns if the summary tables or figures are presented by treatment.

# 5.1 Subject disposition

### 5.1.1 Screen failures

Screen failures will be summarized based on the SCR and will include:

- Number (%) of study subjects who did not successfully complete the screening period (based on 'Was the subject randomized?' recorded as 'No' on the 'Randomization' page).
- Primary reason for screen failure (based on reason entered on the 'Randomization' page).

The eligibility criteria not met will be summarized. All reasons for screen failures will be listed.

Of note, no re-screening is allowed in the study.

\* Regulatory request for both RND and FAS.

# 5.1.2 Study disposition

Study subject disposition will be summarized based on the SCR, presented by treatment sequence and overall, and will include:

- Number of study subjects screened (only for overall column).
- Number (%) of study subjects randomized (based on non-missing randomization number).
- Number (%) of study subjects who received study treatment during the TP I (based on non-missing 'Treatment start date' for TP I on the 'Study Treatment Log' page). Percentage will be based on randomized subjects.
- Number (%) of study subjects who received study treatment during the TP II (based on non-missing 'Treatment start date' for TP II on the 'Study Treatment Log' page). Percentage will be based on randomized subjects.
- Number (%) of study subjects who completed TP I (based on 'Reason for treatment stop' entered as 'Completion as per protocol' for TP I on the 'Study Treatment Log' page). Percentage will be based on study subjects who received study treatment (in TP I).
- Number (%) of study subjects who completed the TP II (based on 'Reason for treatment stop' entered as 'Completion as per protocol' for TP II on the 'Study Treatment Log' page). Percentage will be based on study subjects who received study treatment (in TP II).
- Number (%) of study subjects completing the study (based on 'Did the subject complete the study?' recorded as 'Yes' on the 'End of Study Status' page). Percentage will be based on randomized subjects.
- Number (%) of study subjects completing the washout-period, i.e., subjects being treated in TP I and TP II.

## 5.1.3 Study and study treatment completion/discontinuation

The following summary will be based on the SAF and presented by treatment and overall:

- Number (%) of study subjects who prematurely discontinued study treatment (based on 'Reason for treatment stop' entered as 'Discontinuation' on the 'Study Treatment Log' page).
- Primary reason for premature study treatment discontinuation (based on 'Discontinuation, Reason' entered on the 'Study Treatment Log' page).

The treatment discontinuation table will also be presented by treatment period and treatment based on the SAF.

The following summary will be based on the RND and FAS, and presented by treatment and overall:

- Number (%) of study subjects who prematurely discontinued from the study (based on non-missing reason for stopping study entered on the 'End of Study Status' page).
- Primary reason for premature discontinuation from the study (based on 'Study stopped due to' entered on the 'End of Study Status' page).

The study discontinuation table will also be presented by study period and treatment (TP I, washout-period, TP II, safety follow-up period).

All reasons for premature study treatment discontinuation and study discontinuation will be listed based on the RND.

# 5.1.4 Study enrollment

The number (%) of screened and randomized study subjects will be displayed by site based on the SCR.

The randomization scheme and codes will be listed for randomized study subjects only based on the RND.

#### 5.2 Protocol deviations

The RND will be used for the summary of PDs. All PDs and important PDs will be summarized in separate tables as per pre-specified category (i.e., selection criteria, IMP, study conduct/procedure, forbidden medication, withdrawal criteria and other).

A study subject with multiple occurrences of a PD is counted only once per PD category.

The PD outputs will be summarized by treatment sequence and overall.

A listing of PDs will be provided using the SCR.

# 5.3 Subject characteristics

Unless noted otherwise, summaries and listings described in this section will be based on the RND.

Summaries will be provided by treatment sequence and overall. Data will be listed individually by study subject.

#### 5.3.1 Demographics

Demographic data at Screening, including age, sex, race, and ethnicity, will be summarized (by treatment sequence and overall) based on the RND and FAS, and listed.

The same summary will also be provided for screen failures based on the SCR.

Confidential

Statistical Analysis Plan for Clinical Study Report Version 2 Doc No D-24.149

#### **5.3.2** Baseline disease characteristics

The baseline disease characteristics table will contain a summary of sTST, ISI© score, the ISI© score in categories ( $\leq 14$ , 15-21,  $\geq 22$ ) and the summary of the average number of nocturnal voidings at baseline, as derived by Minze Health [Bladt 2022]. Baseline disease characteristics will be summarized based on the RND and FAS.

Baseline disease characteristics data will be listed based on the RND.

# 5.3.3 Medical history and concomitant diseases at Screening

Relevant medical history and current medical conditions will be coded using MedDRA.

Any disease or diagnosis is defined as previous if 'Ongoing at informed consent' is answered as 'No'; all other diseases/diagnoses are considered as study concomitant (where answer is 'Yes').

Medical history and current (ongoing) medical conditions will be summarized separately and listed (based on the RND). Summaries will be presented for each treatment sequence and overall, by primary SOC and PT. Medical history will be sorted by SOC and PT within each SOC by descending frequency based on all treatment sequences combined.

The MedDRA version used for reporting will be specified in the footnote of the applicable output.

# **5.3.4** Previous and concomitant therapy

Previous and concomitant therapies will be coded using the WHO Drug Global reference dictionary that employs the WHO ATC classification system. The WHO Drug Global version used for reporting will be specified in the footnote of the applicable output.

*Previous therapies* are any treatments for which the end date is prior to the start of study treatment. A previous therapy is to be recorded in the 'Previous/Concomitant Medication' page if discontinued less than 30 days prior to signing of the informed consent form.

Study treatment-concomitant therapies are any treatments that are either ongoing at the start of study treatment or initiated on or after the start of TPI. The use of all treatment-concomitant therapies (including contraceptives and traditional and alternative medicines, e.g., plant-, animal-, or mineral-based medicines) is to be recorded in the 'Previous/Concomitant Medication' page.

Number (%) of study subjects having taken at least one previous or concomitant therapy will be summarized by ATC classification level 4 (or next highest available level) and individual preferred name within each ATC classification based on the SAF. Previous and concomitant therapy will be sorted by ATC class and preferred name within each ATC class by descending frequency based on all treatment sequences combined.

Summary tables will be provided for previous and study treatment-concomitant therapies separately (by treatment sequence and overall). All concomitant therapies will be listed using the SAF and those related to an AE will be flagged.

# 5.4 Study treatment exposure and compliance

Summaries and listings described in this section will be based on the SAF.

# 5.4.1 Exposure

The duration of study treatment (including categories:  $\leq 1, > 1-2, > 2-3, > 3-4, > 4$  weeks) will be summarized based on the SAF, by treatment and overall.

The duration of treatment (in days) is defined as the difference between the treatment end date and the treatment start date plus one day. This calculation ignores periods of treatment interruption.

Due to the cross-over design, the duration of the washout period will also be summarized based on the SAF (only for those subjects who were treated in both treatment periods). The washout period is defined as:

Washout-period (in days) = Treatment start date of TP II – Treatment end date of TP I + 1 day.

The duration of treatment along with the reason for treatment discontinuation will be listed by treatment sequence and period based on the SAF. The duration of the washout period will also be listed based on the SAF.

## **5.4.2** Compliance with study treatment

Study treatment compliance will be assessed through study treatment dispensing and accountability.

The following formula will be used to calculate compliance for the treatment period:

• Study treatment compliance (%) = [(Number of capsules dispensed – Number of capsules returneda) / (Treatment duration – Total duration of treatment interruptions)] × 100.

Treatment duration and total duration of treatment interruptions are calculated using the dedicated eCRF page 'Study Treatment Log'.

<sup>a If a study subject did not return his/her bottle (e.g., it is lost), compliance will not be calculated, and compliance will be set to missing.

Treatment duration is calculated as:

• Treatment duration (days) = Date of last drug intake of study treatment – Date of first drug intake of study treatment + 1 day.

Total duration of treatment interruption (days) is the sum of all the treatment interruptions' durations, calculated as:

• Treatment interruption duration = Date restarted study treatment – End date of study treatment due to an interruption – 1 day.

For example, if a study subject stopped his/her treatment on 19MAR2022 and started again on 23MAR2022, as the treatment is taken on the start and end dates, the calculation will be 23MAR2022 - 19MAR2022 - 1 day = 3 days of interruption. Should the study subject interrupt the treatment again for 7 days, the total duration of interruptions will be 10 days.

Study treatment compliance (including categories 0%, > 0%–< 50%, 50%–< 80%, 80%–< 100%, 100%, > 100%), treatment interruptions (Yes/No), and duration of treatment interruptions will be summarized based on the SAF. The summary table will be repeated by treatment period based on the SAF.

The number (%) of study subjects who have treatment interruptions, and the corresponding reasons will be tabulated based on the SAF.

Study treatment compliance, dispensing and accountability data will be listed based on the SAF.

#### 6 EFFICACY VARIABLES AND ANALYSES

The analyses of efficacy endpoints will be performed using the FAS. Efficacy data described below will be listed using the FAS.

As there were no secondary endpoints defined in the protocol, only the primary endpoint and other efficacy endpoints will be analyzed.

# 6.1 Primary endpoint analysis

All available data for each subject, regardless of intercurrent events, will be used in all statistical analyses, unless otherwise specified.

## 6.1.1 Primary efficacy endpoint

The primary efficacy endpoint of this study is defined as the change from baseline to Week 4 (of both treatment periods) in sTST.

In each treatment period, the change from baselinea to Week 4b in sTST is calculated as follows:

• Change from baseline = Mean value at Week  $4^b$  – Mean value at baselinea.

Changes from baseline in sTST for Weeks 1–3 will be included in the MMRM. Definitions for the changes from baseline will be identical. For Week 1, sTST is averaged across days 2–8, for Week 2 across days 9–15, and for Week 3 across days 16–22.

Subjects must have at least 2 days of data during each week to calculate a weekly mean. Otherwise, the mean value will be considered missing for that week.

For subjects discontinuing a treatment period prematurely (TP I or TP II), all data up to Day 29 will be included to derive the weekly averages (if data is available up to that point). In the event that subjects have extended treatment periods > 4 weeks, only data up to Day 29 will be included in the derivation of the weekly averages.

# **6.1.2** Overall testing strategy

The primary endpoint will be analyzed based on an MMRM. Some sensitivity analyses will also be performed for the primary endpoint. Those analyses are not part of the testing strategy.

Hypotheses are defined as follows:

- H0: Mean of the within-subject changes in sTST from baseline to Week 4 between daridorexant 50 mg and placebo = 0;
- H1: Mean of the within-subject changes in sTST from baseline to Week 4 between daridorexant 50 mg and placebo ≠ 0.

The null hypothesis will be tested at a 2-sided 0.05 significance level.

A preview of the main analyses is given in Table 3 using the estimand terminology [ICH 2019]. Estimands are defined by five attributes: treatment condition of interest, target population, endpoint, strategy for addressing intercurrent events (i.e., premature discontinuation of treatment), and population-level summary.

The primary estimand is based on the primary endpoint: the difference in means between the two treatments in the change from baseline to Week 4 in sTST, regardless of treatment discontinuation. For the primary estimand, the treatment condition is daridorexant 50 mg once daily for up to 4 weeks whereas the alternative condition is placebo once daily for the

<sup>a Baseline is the mean value based on the screening sleep diary for sTST, performed on the 7 days preceding

<sup>b Week 4 is the mean value based on the sleep diary entries for sTST performed on study days 23–29 for each period.

same period. The other four attributes are given in the table below. The primary estimand follows a 'treatment policy' strategy.

The secondary estimand is also based on the primary endpoint. Intercurrent events are defined as premature treatment discontinuations. Details are provided in Table 3. The secondary estimand follows a 'hypothetical' strategy.

Table 3 Estimands for the primary objective

Estimand	Target population	Endpoint	Strategy for addressing intercurrent events	Population-level summary
Primary estimand	Subjects with insomnia associated to nocturia	Change from baseline to Week 4 in sTST	Treatment policy strategy, i.e., endpoint data after premature treatment discontinuation are used.	Treatment effect expressed as difference of LS Mean changes from baseline to Week 4 (daridorexant minus placebo; from MMRM)
Secondary estimand	Subjects with insomnia associated to nocturia	Change from baseline to Week 4 in sTST	Hypothetical strategy, i.e., endpoint data after premature treatment discontinuation are not used.	Treatment effect expressed as difference of LS Mean changes from baseline to Week 4 (daridorexant minus placebo; from MMRM)

LS Mean = least squares mean; MMRM = mixed model for repeated measures; sTST = subjective total sleep time.

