Treatment period preference										Х	X ³	
Narrative		Х			Х					Х	X ³	
Study treatment dispensing/return			Х		Х			Х		Х	X ³	
Study drug intake			•		►			-		► ►		
Treatment acco	ountability				Х					Х	X ³	
SAEs/AEs ¹		•										

¹ All AEs and SAEs that occur after signing the ICF and up to 5–10 days after study treatment discontinuation must be reported [see also Section 8.1 and 8.2].

² Must be done before randomizing the subject.

³ Only applicable for subjects who prematurely discontinued study treatment. All subjects withdrawn from study treatment will be encouraged to follow planned study procedures (e.g., visits, diary and questionnaire completion until planned EOS visit) provided that the subject's consent for this limited participation in the study has not been withdrawn.

⁴Will be completed by phone call.

⁵PGA-S and PGI-C (daytime symptoms and nighttime symptoms questionnaires) will be completed at home once a week between Visit 2 and Visit 8. The patient global scales are completed on the same days.

⁶The hand-held device is handed out to the subject and completed at home daily from Visit 1 to Visit 8.

Daridorexant (ACT-541468)	
Insomnia and comorbid nocturia	
Protocol ID-078A401	Confidential
Version 3	
4 September 2023, page 30/122	

⁷The voiding diary must be completed by the subjects for 3 consecutive days and nights after the Visit 1, Visit 2 and Visit 6 as well as for 3 consecutive days and nights immediately preceding Visit 4 and Visit 8, respectively [see Table 2]. The investigator should plan the completion of the diary according to the visit schedule.

⁸The IDSIQ will be administered from Visit 1 to Visit 8 and completed daily.

⁹The ICIQ-MLUTS will only be given to male subjects, while females will receive the ICIQ-FLUTS.

*The site will contact the subject to remind him/her to complete the voiding diary for 3 consecutive days preceding the EOTP visit.

** The subject will be asked to return for a PEOT visit within 5 days of last intake of study treatment and thereafter to attend the following visits up to the respective EOTP visit.

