4.1.1 Study periods for an individual subject

Screening period: Starts with the full signature of the ICF at Visit 1 and lasts 14–21 days. All baseline assessments and eligibility checks will be done during this period.

Treatment period (Periods I and II): Randomization will take place on Day 1 (Visit 2) after confirmation that all eligibility criteria have been met, prior to the first study drug administration of Treatment Period I. The double-blind cross-over phase will consist of 2 treatment periods of 29 days \pm 2 days each that are separated by a washout period of 14–21 days. EOTP I and EOTP II is reached on the morning after last treatment intake in the evening of the respective treatment period. Each subject will be randomized in a 1:1 ratio to one of the treatment sequences defined as:

- Treatment A: 50 mg daridorexant, followed by Treatment B: placebo
- Treatment B: Placebo, followed by Treatment A: 50 mg daridorexant

Follow-up and Washout period:

The follow-up period, to detect any safety events related to the cessation of study treatment, starts after completion of the EOTP I and EOTP II visit of each treatment period (I and II) and lasts for 5–10 days.

For period I, the first 5–10 days of the washout period overlap with the follow-up period and are followed by an additional 9–16 days of washout, for a total of 14–21 days washout period before entering treatment period II.

A subject's participation in the study ends with the completion of the EOS phone call 5–10 days after EOTP II (Visit 9) of Period II [Table 1].

The visit schedule and protocol-mandated procedures are performed according to the schedule of activities [Table 1] and are described in Section 3.2, 3.3, and 7.2.

The overall study design is depicted in Figure 1.

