9.2.2.2 Variable definition (sTST)

The change from Baseline^a to Week 4^b in sTST is calculated as follows:

Change from Baseline = Averaged value at Week 4 – Averaged value at Baseline.

^a Baseline is the mean value based on the screening sleep diary for sTST, performed on the 7 days preceding Randomization.

^b 'Week 4' is the mean value based on the sleep diary entries for sTST performed on study days 23–29 for each period. Data after the EOTP I/II visits will not be included in the analysis, as subjects are expected to be on double-blind treatment up to that point.

As sTST for Weeks 1–3 will also be included in the MMRM, definitions for the changes from baseline will be identical. For Week 1, sTST is averaged across days 2–8, for Week 2 across days 9–15, and for Week 3 across days 16–22.

Subjects must have at least 2 days of data during each week to calculate a weekly mean. Otherwise, the mean value will be considered missing for that week.

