## 10.2 Study periods

The screening period is defined as the time from the informed consent date until one day before the study treatment start date of TP I, or date of screening failure.

The treatment periods are defined as the time from the day of study treatment start until the day of EOT (Week 4), or, for those who prematurely discontinued study treatment (i.e., those without an EOT date), until the day of study treatment end date.

Provided the subject starts the second treatment, the washout period is defined as the time from one day after the end of TP I until the day before start of TP II.

The safety follow-up period is defined as the time from one day after the end of the last treatment period until end of safety follow-up period / EOS date (for both treatment periods).

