## 10.5 Change from baseline

The change from baseline is defined as the post-baseline value (any assessment performed after baseline and up to EOS) minus the baseline value. A positive number indicates an increase compared to baseline.

Page 40/50

Statistical Analysis Plan for Clinical Study Report Version 2 Doc No D-24.149

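### The SAP's Week 4 sTST window omits the protocol's EOTP cut, and its VAS windows for Weeks 2 and 3 span 8 and 6 days instead of 7.

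*SAP*

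**What the plan says.** **Week 4 sTST.** Protocol 9.2.2.2 and the synopsis define Week 4 as study days 23–29 of each period and add a limit: "Data after the EOTP I/II visits will not be included in the analysis". Footnote b of SAP 6.1.1 (printed under 6.1.2) keeps the days without the limit: "Week 4 is the mean value based on the sleep diary entries for sTST performed on study days 23–29 for each period". The SAP's own limits are at Day 29. Subjects who stop a period early contribute everything up to Day 29, and for periods longer than 4 weeks "only data up to Day 29 will be included in the derivation of the weekly averages". SAP 11.1 declares no change to the planned analyses, and SAP 11.3 does not mention this one.

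**Timing.** Visits 4 and 8 fall on Day 29 ± 2 (Protocol Table 1). Protocol 4.1.1 states that "EOTP I and EOTP II is reached on the morning after last treatment intake in the evening of the respective treatment period". Under Table 1, footnote 6, the diary is "completed at home daily from Visit 1 to Visit 8", so it continues through the washout after Visit 4 and stops at Visit 8.

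**VAS.** Protocol 3.2.1 requires 7-day averages for all sleep-diary endpoints. SAP 6.3.1.2.1 assigns Days 2–8, 9–16, 17–22 and 23–29 to Weeks 1–4. For sTST (6.1.1) and IDSIQ (6.3.3.5.1), the SAP uses Days 2–8, 9–15, 16–22 and 23–29. Number of awakenings (6.3.1.3) and morning sleepiness (7.6) take their definitions from the VAS section.

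**The concern.** The protocol drops nights after EOTP because treatment has ended by then. Without that rule, a subject who completes Period I on schedule on Day 27 or 28 brings washout nights into the primary endpoint. Only subjects who receive daridorexant first lose drug effect this way, so the treatment difference is pulled toward zero.

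The estimand strategies do not deal with these nights. The SAP's intercurrent event is premature discontinuation, and finishing on Day 27 is completion within the visit window. The hypothetical (secondary) estimand therefore keeps the nights too.

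The sensitivity analysis in SAP 6.1.6.2 is affected more. It removes the 3 urine-collection nights just before Visit 4, all of them treated, so the untreated nights weigh more in what is left. It would then differ from the primary analysis for a reason unrelated to urine collection, which is the only question it is meant to answer.

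The VAS windows put Day 16 in Week 2 instead of Week 3 for six diary variables: four efficacy VAS, awakenings and morning sleepiness. Their Week 2 and Week 3 values then cover different days from sTST and IDSIQ.

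**Working it through.** **1. The plan's own power.** Inputs from Protocol 9.4: difference 26 min (fallback 20 min), SD of the within-subject difference 44 min, n = 50, two-sided 0.05, paired t-test. The noncentral t distribution gives 98.4% at 26 min and 88.3% at 20 min, consistent with the stated levels of at least 90% and at least 80%.

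**2. Untreated entries in Days 23–29, Period I.** A morning entry describes the night before, so entries dated after the EOTP visit describe untreated nights.

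| EOTP I | Untreated, primary | Entries left in 6.1.6.2 | Untreated, 6.1.6.2 |
|---|---|---|---|
| Day 27 | Days 28, 29: 2 of 7 | Days 23, 24, 28, 29 | 2 of 4 |
| Day 28 | Day 29: 1 of 7 | Days 23, 24, 25, 29 | 1 of 4 |
| Days 29–31 | 0 of 7 | – | 0 |

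The 6.1.6.2 counts are the same if the removed entries are dated one day earlier. In Period II the diary ends at Visit 8, so no such entries arise.

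**3. Dilution.** Let f27 and f28 be the shares of Period I EOTP visits on Days 27 and 28. The documents do not give them, so they are assumed. Untreated nights are taken as equal to placebo nights. Only half the subjects (daridorexant first) lose effect, hence the factor 0.5:

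Effect = E × [1 − 0.5 × (2·f27 + f28) / m], with m = 7 (primary) or 4 (6.1.6.2).

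| Assumed EOTP I spread | E (min) | Primary (power) | 6.1.6.2 | Gap |
|---|---|---|---|---|
| 10% on Day 27, none on Day 28 | 26 | 26 × (1 − 0.1/7) = 25.63 (98.1%) | 26 × (1 − 0.1/4) = 25.35 | 0.28 |
| Uniform over Days 27–31 | 26 | 26 × (1 − 0.3/7) = 24.89 (97.5%) | 26 × (1 − 0.3/4) = 24.05 | 0.84 |
| Uniform over Days 27–31 | 20 | 20 × (1 − 0.3/7) = 19.14 (85.4%) | – | – |
| All on Day 28 | 26 | 24.1 (96.7%) | – | – |
| All on Day 28 | 20 | 18.6 (83.3%) | – | – |
| All on Day 27 (extreme) | 26 | 22.3 (93.9%) | – | – |
| All on Day 27 (extreme) | 20 | 17.1 (77.1%) | – | – |

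A simulation of the two sequences with uniform EOTP (20,000 runs, period-adjusted) gives power of 97.4% at 26 min and 85.7% at 20 min, in line with the formula.

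**4. Precision lost by applying the cut.** Affected subjects keep 5 or 6 of 7 nights in Period I. With uniform EOTP and an assumed night-to-night SD s:

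SD = √{44² + s² × [0.2 × (1/5 − 1/7) + 0.2 × (1/6 − 1/7)]}.

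For s = 45 min, SD = 44.4 and power at 26 min is 98.2%. For s = 75 min, SD = 45.0 and power is 97.9%. Without the cut, power under the same spread is 97.5%.

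**5. VAS windows (last day − first day + 1).** Week 1: 8 − 2 + 1 = 7. Week 2: 16 − 9 + 1 = 8. Week 3: 22 − 17 + 1 = 6. Week 4: 29 − 23 + 1 = 7. The sTST and IDSIQ windows give 7 in every week.

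**The case against.** The strongest reply is that the cut is already implied. SAP 6.1.1 works within each treatment period. SAP 10.2 ends a completer's period on the day of EOT and starts the washout the next day, so after an EOTP on Day 27, Days 28 and 29 are washout by the SAP's own definition. The two Day 29 sentences concern premature discontinuers and extended periods, not early completers. The SAP is based on protocol Version 3 and declares no change, which also fits the cut still being in force.

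This reading is possible, and it is partial support for a cut. It does not settle the matter, because 6.1.1 never refers to 10.2. The general rules also lean the other way: SAP 6.1 says "All available data for each subject, regardless of intercurrent events, will be used in all statistical analyses, unless otherwise specified", and SAP 10.5 admits "any assessment performed after baseline and up to EOS". Neither is decisive, since 6.1 is qualified and 10.5 is generic, but a programmer working from footnote b would average Days 23–29.

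The second reply is size, and it stands. The standard error of the paired difference is 44/√50 = 6.2 min. A loss of 0.4 to 1.1 min is 0.06 to 0.18 of that, and it cannot produce a false positive. The planned visit is Day 29, so even the uniform spread may overstate early visits.

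On the VAS windows, they leave no gap or overlap, and the variables concerned are outside the testing strategy. That limits the consequence but does not make the windows right.

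**Conclusion.** Both points hold. As written, the SAP's rule for the primary variable lacks an exclusion that the protocol states, and the change is not declared. Under the assumed spreads (10% of Period I EOTP visits on Day 27, or uniform over Days 27–31), the estimate moves from 26 min to 25.6 or 24.9 min. The missing cut alone separates the primary and urine-night estimates by 0.3 to 0.8 min. Both stated power levels hold under these spreads. Power falls below a stated level only at the 20-min fallback with every Period I EOTP on Day 27 (77.1%). All these sizes assume that untreated nights resemble placebo nights. The case for correction is agreement between the SAP and the protocol on the primary endpoint, not loss of power.

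The VAS windows for Weeks 2 and 3 contradict both the protocol and the rest of the SAP, and the error reaches six variables. Week 4, the primary endpoint and the protocol's morning-sleepiness endpoint (change to EOTP) are not touched by it.

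**What to change.** 1. Add to SAP 6.1.1, and apply in 6.1.6.2: *Diary entries after the EOTP visit of that period are excluded, also when EOTP occurs before Day 29. Data of premature discontinuers are kept up to their EOTP visit, at most Day 29. If no EOTP visit takes place, the limit is Day 29.*
2. In SAP 6.3.1.2.1, set Week 2 to Days 9–15 and Week 3 to Days 16–22. Awakenings and morning sleepiness then follow by cross-reference.

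The cost is SAP wording and programming. For the primary analysis, the nights given up cost less power than the dilution they remove (step 4 of the working). In 6.1.6.2, a subject with EOTP I on Day 27 keeps exactly 2 nights, the SAP's minimum for a weekly mean, so one missed entry makes that Week 4 value missing there. The VAS correction costs nothing further.
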